Deep vein thrombosis will be diagnosed if duplex ultrasound, magnetic resonance venogram (MRV), or venogram is definite or probable positive. Site investigators will record if location is proximal or distal. Pulmonary embolism will be diagnosed with a high probability ventilation perfusion lung scan, CT scan, or pulmonary angiogram.

ix Bleeding

Major bleeding will be defined as 1) fatal bleeding, and/or 2) symptomatic bleeding in a critical area or organ, such as intracranial, intraspinal, intraocular, retroperitoneal, intra- articular or pericardial, or intramuscular with compartment syndrome, and/or 3) bleeding causing a drop in hemoglobin concentration of 2 g/dL or greater (62) from the last hemoglobin concentration prior to randomization to the nadir hemoglobin concentration during hospitalization or up to 30 days post randomization. The drop in hemoglobin concentration will account for each unit of red blood cell transfusion transfused by subtracting 1 g/dL for each unit administered.

x Infections

x.1 Pneumonia

Pneumonia will be diagnosed using CDC criteria (48) which includes radiographic abnormalities and combination of symptoms (i.e., cough), signs (i.e., fever, tachypnea, or laboratory abnormalities (i.e., white blood cell count, hypoxemia).

x.2 Blood Stream Infection

Blood stream infection will be defined using CDC criteria which includes a recognized pathogen cultured from 1 or more blood cultures and organism cultured from blood is not related to an infection at another site, at least 1 of the following signs or symptoms: fever, chills, or hypotension and signs

and symptoms and positive laboratory results are not related to an infection at another site and common skin contaminant is cultured from 2 or more blood cultures drawn on separate occasions.

x.3 Urinary Tract Infection

Urinary Tract Infection will be defined using CDC criteria (48) which include one of the following signs or symptoms: fever (>38.0°C) or localized pain or tenderness, and laboratory evidence for infection.

xi Length of Stay and Intensive Care Unit Days

The trial will collect the number of days post randomization that patient is in the hospital and in intensive care unit.

xii Quality of Life

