Event rates, the relative risk and the absolute difference between transfusions strategy groups for the dichotomous secondary and tertiary outcomes will be calculated with their 95% confidence intervals using log-binomial regression methods accounting for clinical site with random effects. The length of hospital stay from randomization and from admission will be analyzed using non-parametric Wilcoxon

rank sum tests, and long-term mortality will be analyzed with Kaplan-Meier methods and the log rank statistic. The Kaplan-Meier estimated mortality rate in each treatment group at 180 days, the absolute difference between the assigned treatment groups at 180 days, and the 95% confidence interval for the difference will be presented. Transfusion strategy comparisons of the EQ-5D quality life measures at 30 days will be based on t-tests or the Wilcoxon rank sum test. No adjustment of the alpha level will be made for the secondary and tertiary analyses. Rather the results will be interpreted based upon the observed findings, their designation as secondary or tertiary outcomes, and in comparison to the primary outcome result.

The secondary outcomes include: 1) all-cause mortality within 30 days; 2) myocardial reinfarction within 30 days; and 3) the composite outcome of all-cause mortality, nonfatal myocardial reinfarction, ischemia driven unscheduled coronary revascularization (percutaneous coronary intervention or coronary artery bypass grafting), or readmission to the hospital for ischemic cardiac diagnosis within 30 days.

The tertiary outcomes include: 1) all-cause mortality, nonfatal myocardial reinfarction, and unstable angina (i.e. acute coronary syndrome) 2) ischemia driven unscheduled coronary revascularization within 30-days; 3) readmission to the hospital for ischemic cardiac diagnosis, 4) congestive heart failure within 30 days; 5) unscheduled readmission to hospital for any reason within 30 days; 6) each of the individual cardiovascular outcomes of stroke, pulmonary embolism or deep venous thrombosis, and bleeding within 30 days; 7) each of the individual infectious outcomes of pneumonia, blood stream, and urinary tract within 30 days; 8) each of the individual in-hospital outcomes of length of hospital stay post randomization and number of days in intensive care unit; 9) patient reported quality of life measures based on the EuroQol questionnaire (EQ-5D) at 30 days; and 10) all-cause mortality at 6-months.

4.e Missing Outcome Data

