## **Tertiary Aims**

- 1) To determine whether a liberal (10g/dL) transfusion strategy reduces all-cause mortality, nonfatal myocardial reinfarction, or unstable angina (i.e. acute coronary syndrome) within 30 days, compared to a restrictive transfusion strategy.
- 2) To determine whether a liberal (10g/dL) transfusion strategy reduces ischemia driven unscheduled coronary revascularization within 30-days compared to a restrictive strategy.
- 3) To determine whether a liberal (10g/dL) transfusion strategy reduces unscheduled readmission to hospital for ischemic cardiac diagnosis within 30 days, compared to a restrictive strategy.
- 4) To determine whether a liberal (10g/dL) transfusion strategy increases congestive heart failure within 30 days, compared to a restrictive transfusion strategy.
- 5) To determine whether a liberal (10g/dL) transfusion strategy reduces unscheduled readmission to hospital for any reason within 30 days, compared to a restrictive strategy.
- 6) To determine whether a liberal (10g/dL) transfusion strategy increases each of the individual thrombotic/hemorrhagic outcomes of stroke, pulmonary embolism or deep venous thrombosis, and bleeding within 30 days, compared to a restrictive strategy.

- 7) To determine whether a liberal (10g/dL) transfusion strategy increases each of the individual infectious outcomes of pneumonia, blood stream, and urinary tract within 30 days, compared to a restrictive strategy.
- 8) To determine whether a liberal (10g/dL) transfusion strategy reduces each of the individual in-hospital outcomes of length of hospital stay post randomization and number of days in intensive care unit, compared to a restrictive strategy.
- 9) To determine whether a liberal (10g/dL) transfusion strategy increases patient reported quality of life using the EuroQol questionnaire (EQ-5D) at 30 days compared to a restrictive strategy
- 10) To determine whether a liberal (10g/dL) transfusion strategy reduces all-cause mortality at 6-months following randomization, compared to a restrictive strategy.

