Congestive Heart Failure: Sites personnel will use 2014 ACC/AHA Key Data Elements and Definitions for Cardiovascular Endpoint Events in Clinical Trials to define congestive heart failure. New or worsening symptoms of congestive heart failure on presentation (increasing dyspnea, paroxysmal nocturnal dyspnea, orthopnea), has objective evidence of new or worsening heart failure, and receives initiation or intensification of treatment specifically for heart failure.

TIA or Stroke: The 2014 ACC/AHA Key Data Elements and Definitions for Cardiovascular Endpoint Events in Clinical Trials will be used to define stroke. A transient ischemic attack (TIA) is defined as “a transient episode of focal neurological dysfunction caused by brain, spinal cord, or retinal ischemia, without acute infarction.” Stroke is defined on the basis of the presence of acute infarction as demonstrated by imaging or based on the persistence of symptoms more than 24 hours.

Deep Venous Thrombosis or Pulmonary Embolism: Deep vein thrombosis will be diagnosed if duplex ultrasound, magnetic resonance venogram (MRV), or venogram is definite or probable positive. Site investigators will record if location is proximal or distal. Pulmonary embolism will be diagnosed with a high probability ventilation perfusion lung scan, CT scan, or pulmonary angiogram.

Bleeding: Major bleeding will be defined as 1) fatal bleeding, and/or 2) symptomatic bleeding in a critical area or organ, such as intracranial, intraspinal, intraocular, retroperitoneal, intra-articular or pericardial, or intramuscular with compartment syndrome, and/or 3) bleeding causing a drop in hemoglobin concentration of 2 g/dL or greater from the last hemoglobin concentration prior to randomization to the nadir hemoglobin concentration during hospitalization or up to 30 days post randomization. The drop in

hemoglobin concentration will account for each unit of red blood cell transfusion transfused by subtracting 1 g/dL for each unit administered.

Infections recorded include pneumonia and blood stream infections.

Pneumonia: Pneumonia will be diagnosed using CDC criteria which includes radiographic abnormalities and combination of symptoms (i.e., cough), signs (i.e., fever, tachypnea, or laboratory abnormalities (i.e., white blood cell count, hypoxemia).

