## **Analysis of Secondary and Other Outcomes**

All of the secondary outcomes and most of the tertiary outcomes are dichotomous endpoints (i.e. presence/absence of an event during the 30-day study period). The pre-defined secondary outcomes are: 1) all-cause mortality within 30 days; 2) myocardial reinfarction within 30 days; and 3) the composite outcome of all-cause mortality, nonfatal myocardial reinfarction, ischemia driven unscheduled coronary revascularization (percutaneous coronary intervention or coronary artery bypass grafting), or readmission to the hospital for ischemic cardiac diagnosis within 30 days. Other dichotomous outcomes include: 1) all-cause mortality, nonfatal myocardial reinfarction, and unstable angina (i.e. acute coronary syndrome) 2) ischemia driven unscheduled coronary revascularization within 30-days; 3) readmission to the hospital for ischemic cardiac diagnosis, 4) congestive heart failure within 30 days; 5) unscheduled readmission to

hospital for any reason within 30 days; 6) each of the individual cardiovascular outcomes of stroke, pulmonary embolism or deep venous thrombosis, bleeding, and cardiac death within 30 days; 7) each of the individual infectious outcomes of pneumonia and blood stream infections within 30 days.

For each of the dichotomous endpoints listed above, the observed proportion of patients who experience the endpoint in each assigned group, the risk ratio (Restrictive versus Liberal) and 95% confidence interval, the risk difference (Restrictive – Liberal) and 95% confidence intervals will be calculated and presented (Table 2). Superiority of either transfusion strategy for each endpoint will first be evaluated using a two-sided test with  $\alpha=0.05$ . If superiority is not detected, the non-inferiority of the Restrictive strategy will be assessed using a 15% relative non-inferiority margin; that is, the Restrictive strategy will be deemed non-inferior for a given dichotomous endpoint when the entire 95% confidence interval for the estimated RR is  $< 1.15$ . For the 30-day dichotomous outcomes, all available data from randomization through 30 days will be used to identify outcomes. Patients with incomplete follow-up will be assumed to have no event after the time of last contact for these analyses.

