**Table 2: MINT Trial Outcomes**

Characteristic	Cumulative Events at 30 days (Patient-Level)				
	Restrictive (N=)	Liberal (N=)	Risk Difference* (95% CI)	Risk Ratio* (95% CI)	p-value
Primary Outcome (at 30 days)					
All-cause mortality/adjudicated myocardial infarction (MI), n (%)					
Secondary Outcome (at 30 days)					
All-cause mortality, n (%)					
Adjudicated myocardial infarction, n (%)					
All-cause mortality, adjudicated MI, ischemia driven unscheduled revascularization, unscheduled readmission to the hospital for ischemic cardiac diagnosis, n (%)					
Other Outcome (at 30 days)					
All-cause mortality, adjudicated non-fatal MI, unstable angina, n (%)					
Ischemia driven unscheduled revascularization, n (%)					
Unscheduled readmission to the hospital for ischemic cardiac diagnosis, n (%)					
Heart Failure, n (%)					
Unscheduled readmission to hospital for any reason, n (%)					
Stroke, n (%)					
Pulmonary embolism or deep vein thrombosis, n (%)					
Bleeding event, n (%)					
Cardiac Death, n (%)					
Pneumonia or bacteremia, n (%)					

\* Risk Difference = Restrictive - Liberal for event outcomes

Risk Ratio = Restrictive / Liberal for event outcomes

Restrictive is considered non-inferior to Liberal if the upper bound of the Risk Ratio 95% Confidence Interval is <1.15

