## Supplementary Information: Other 30-day Outcomes and Adverse Events

Characteristic	Cumulative Rate of Event at 30 days (Patient-Level)	
	Restrictive (N=)	Liberal (N=)
Outcome Events		
New suspected MI, n (%)		
Procedures: PCI, n (%)		
Ischemia driven unscheduled PCI, n (%)		
Procedures: CABG, n (%)		
Ischemia driven unscheduled CABG, n (%)		
New unstable angina, n (%)		
Transient Ischemic Attack (TIA), n (%)		
Any indication of Heart Failure, n (%)		
Any Indication of TACO, n (%)		
Strict Definition of TACO, n (%)		
Arrhythmias		
Atrial fibrillation/flutter, n (%)		
Supraventricular tachycardias other than atrial fibrillation, n (%)		
Paroxysmal supraventricular tachycardia, n (%)		
Ventricular tachycardia, n (%)		
Ventricular fibrillation, n (%)		
Cardiac arrest, n (%)		
Mobitz type 1 AV block, n (%)		
Mobitz type 2 AV block, n (%)		
Complete (3rd degree) AV block, n (%)		
Right bundle branch block, n (%)		
Left bundle branch block, n (%)		
Bifascicular block, n (%)		
Asystole, n (%)		
Multifocal atrial tachycardia, n (%)		
Nonparoxysmal junctional tachycardia, n (%)		
Thrombotic/Ischemic Events and Complications of MI		
Chest pain or stable angina, n (%)		
Mechanical complications of MI, n (%)		
Pericarditis, n (%)		
Pericardial effusion/tamponade, n (%)		
Syncope, n (%)		
Cardiomyopathy, n (%)		
Cardiogenic Shock, n (%)		
Other Adverse Events		
Acute respiratory failure, n (%)		
Acute renal failure, n (%)		
Transfusion Reactions		
Transfusion related acute lung injury, n (%)		
Acute hemolytic transfusion reaction, n (%)		
Transfusion associated sepsis, n (%)		
Anaphylactic transfusion reaction, n (%)		

Characteristic	Cumulative Rate of Event at 30 days (Patient-Level)	
	Restrictive (N=)	Liberal (N=)
Urticarial transfusion reaction, n (%)		
Febrile non-hemolytic reaction, n (%)		
Other Infections		
Urinary tract infection, n (%)		
Septic shock, n (%)		
Clostridium, n (%)		
Cellulitis, n (%)		
Endocarditis, n (%)		
Mediastinitis, n (%)		
Osteomyelitis, n (%)		
Sinusitis, n (%)		
Influenza, n (%)		
Gastroenteritis, n (%)		

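### The SAP's infection aim names three infections individually, but its definitions and comparison list omit urinary tract infection and its Table 2 template merges the other two

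*SAP*

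**What the plan says.** Three places commit to three separate infection comparisons. The protocol's tertiary aim 7 (C3) does so, its list of tertiary outcomes for analysis (F4, 4.d) has "each of the individual infectious outcomes of pneumonia, blood stream, and urinary tract within 30 days", and the SAP's own aim 7 (section 2, Tertiary Aims) asks whether the liberal strategy "increases each of the individual infectious outcomes of pneumonia, blood stream, and urinary tract within 30 days". The protocol also defines the third infection (E7, 7.a, x.3): "Urinary Tract Infection will be defined using CDC criteria (48) which include one of the following signs or symptoms".

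The rest of the SAP does not follow that aim:

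- Section 3 (Definitions of Outcomes) states "Infections recorded include pneumonia and blood stream infections" and defines only those two.
- Section 6 (Analysis of Secondary and Other Outcomes) lists "each of the individual infectious outcomes of pneumonia and blood stream infections within 30 days".
- The next paragraph of section 6 sets the analysis: "For each of the dichotomous endpoints listed above, the observed proportion of patients who experience the endpoint in each assigned group", together with the risk ratio and risk difference and their 95% intervals, shown in Table 2.
- The Table 2 template has one infection row, "Pneumonia or bacteremia, n" (%).
- The supplementary table of other 30-day outcomes and adverse events has "Urinary tract infection, n" (%) under Other Infections. Its only result columns are Restrictive and Liberal.

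**The concern.** The aim, the definitions, the comparison list and the table shells describe three different sets of infection outcomes. A programmer working from the Table 2 shell would produce a different result from one working from the section 6 text. Someone working from the aim would look for a urinary tract comparison that neither supplies.

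This matters because infection is one of the ways the protocol says transfusion could do harm: C4 gives immunosuppression leading to infection, and D2, 2.f repeats the point for bacterial infection. Aim 7 is framed as a harm aim. If the shells are followed, one of its three components has no effect estimate. The other two are shown only as a combined endpoint that no aim or outcome list specifies, and differing effects on pneumonia and blood stream infection would not be visible in it. The Table 2 footnote would also attach its 1.15 non-inferiority reading to that combined endpoint.

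The SAP describes itself as consistent with the protocol, and it explains other departures, such as the added futility analysis and the restriction of the race and ethnicity subgroups. It does not explain this one.

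**Working it through.** The plan states no figure for infection, so there is none to reproduce. The main check sets the sections side by side.

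| Infection | Protocol C3 and F4 4.d | SAP aim 7 | SAP section 3 definition | SAP section 6 comparison list | Table 2 row | Supplementary table |
|---|---|---|---|---|---|---|
| Pneumonia | individual | individual | yes | individual | merged | no row |
| Blood stream | individual | individual | yes | individual | merged | no row |
| Urinary tract | individual | individual | none | absent | none | counts by arm only |

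Two separate mismatches follow.

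1. **Urinary tract infection.** It is in the aim but missing from the SAP definitions and the comparison list. The section 6 commitment to a risk ratio, risk difference and intervals applies to the endpoints listed there, so it does not reach this outcome. What remains is n (%) by arm.
2. **Pneumonia and blood stream infection.** The text requires separate estimates, but no template row holds either one. Here the shell contradicts the text; the text itself is sound.

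**Would separate rows be informative?** The documents give no infection rates, so the event rate p is an assumption and a range is shown. Take n = 1750 per arm (3500 / 2, ignoring missing data) and equal risks in both arms.

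SE(log RR) = sqrt(2 × (1/(np) − 1/n)); 95% limits around RR = 1 are exp(±1.96 × SE).

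- p = 2%: np = 35; SE = sqrt(2 × (1/35 − 1/1750)) = 0.237; limits 0.63 to 1.59
- p = 5%: np = 87.5; SE = sqrt(2 × (1/87.5 − 1/1750)) = 0.147; limits 0.75 to 1.33
- p = 10%: np = 175; SE = sqrt(2 × (1/175 − 1/1750)) = 0.101; limits 0.82 to 1.22

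At each of these rates the upper limit is above 1.15. An observed risk ratio of 1 would therefore not meet the SAP's non-inferiority margin. The value of separate rows lies in the estimates and intervals, more than in the non-inferiority verdict.

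**The case against.** The strongest reply is that this is a drafting slip at the tertiary level. The section 6 text still calls for pneumonia and blood stream infection individually, and the SAP Introduction describes the tables as proposed templates, so a template row should not override the text. Urinary tract infection is still tabulated by arm, and a crude risk ratio with an interval can be computed from those counts. SAP section 6 (Trial Outcome Analyses) applies two-sided tests to all aims, and aim 7 still contains urinary tract infection. The protocol's 4.d also promises relative risks and differences with intervals for dichotomous tertiary outcomes. On this reading the commitment is inconsistent but has not been withdrawn.

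Most of that stands, and it rules out two stronger readings. A reader might infer that aim 7 can no longer be answered. The documents do not support this: two components keep a specified individual analysis, and the third keeps its counts. A reader might also infer selective outcome reporting. All three infections stay scheduled for reporting by arm in some form, and nothing in the documents suggests the change was driven by results.

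The reply does not remove the mismatch. A general statement about testing all aims does not put urinary tract infection on the list that receives estimates, or supply the missing SAP definition. The templates are part of the SAP, and as drawn they have no place for the separate estimates the text requires.

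**Conclusion.** The point holds as an internal inconsistency that leaves a stated harm comparison incomplete. Followed as written, the SAP yields no risk ratio, risk difference, interval or p-value for urinary tract infection. Its main results table shows a combined endpoint in place of two individual ones, and no reason is given for either change.

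The size is small. The outcomes are tertiary, the primary conclusion is unaffected, and the missing comparison could be rebuilt roughly from the planned counts. How precise the separate estimates would be depends on infection rates that the documents do not give. The intervals above rest on assumed rates of 2% to 10%, equal risks and full follow-up of 1750 per arm, and at lower rates they would be wider. They show what separate rows could offer and do not measure the harm done by the inconsistency.

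**What to change.** - In SAP section 3, add urinary tract infection with the protocol's definition (E7, 7.a, x.3) and correct the sentence on which infections are recorded.
- In SAP section 6, add urinary tract infection to the list of dichotomous outcomes.
- In Table 2, give pneumonia, blood stream infection and urinary tract infection one row each, with risk difference, risk ratio and 95% interval. If the combined pneumonia or bacteremia row is wanted, keep it as an extra and label it as added in the SAP.

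If the narrowing was intended, the consistent alternative is to amend aim 7, state the reason and still split the Table 2 row. Restoring the outcome is preferable because it keeps the harm aim as pre-specified.

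The cost is SAP wording and table rows. The supplement already plans urinary tract counts by arm, so no new data collection is implied. There is one small statistical cost: urinary tract infection becomes one more tertiary endpoint with an unadjusted superiority test and, if that is negative, a 1.15 non-inferiority assessment. Keeping the combined row as well adds another comparison of the same kind, so it should be marked as supplementary.

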## **Participant Follow-up**

At hospital discharge, death or 30 days post randomization, whichever comes first, the study staff submit data related to the hospitalization including health status, laboratory results, blood transfusions, and post randomization clinical events. Study staff contact the patient at 30 days post-randomization to ascertain vital status, administer the quality-of-life questionnaire, and determine if there has been a subsequent hospital admission or emergency room visit. Study staff obtain and review the medical records for each readmission and record relevant data and study outcomes. If an acute coronary syndrome event is suspected from the time of randomization until 30-days post-randomization, the staff submits documentation for central review. Study staff contact participants at 6 months following randomization to ascertain the patient's vital status.

Recurrent myocardial infarction is diagnosed when a suspected myocardial ischemic event is reported by the investigators at the clinical sites and confirmed by the Clinical Event Committee. In addition to adjudication of site suspected events, the trial has a surveillance process in which all cardiac troponin values are reviewed by the Clinical Event Committee to detect abnormal biomarker patterns. When criteria are met, the Clinical Event Committee requests that the site submit medical records and ECGs that are temporally related to the abnormal values. The Clinical Events Committee adjudicates occurrences of myocardial infarction, masked to assigned transfusion strategy, from randomization through 30-days post-randomization. Myocardial infarction is classified according to MI type as specified in the 3rd Universal Definition of Myocardial Infarction and whether MI type was ST segment elevation MI (STEMI) non-ST segment elevation MI (NSTEMI), or cannot be determined.

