Blood Stream Infection: Blood stream infection will be defined using CDC criteria which includes a recognized pathogen cultured from 1 or more blood cultures and organism cultured from blood is not related to an infection at another site, at least 1 of the following signs or symptoms: fever, chills, or hypotension and signs and symptoms and positive laboratory results are not related to an infection at another site and common skin contaminant is cultured from 2 or more blood cultures drawn on separate occasions.

Length of Stay and Intensive Care Unit Days: The trial records the number of days post randomization that the patient is in the hospital and in intensive care unit.

Quality of Life: The EuroQol questionnaire (EQ-5D), a standardized instrument that measures health related quality of life in 5 dimensions: mobility, self-care, usual activities, pain/discomfort and anxiety/depression, is used as a measure of patient perceived global health status 30 days after randomization. The EQ-5D utility index value and health today scores will be reported.

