The length of hospital stay from randomization to discharge and the number of days in the ICU from randomization to discharge will be described as a mean (sd) or median (first and third quartile) in each assigned group and the difference will be analyzed using non-parametric Wilcoxon rank sum tests (see for example, Table 3). The mean (sd) or median (first and third quartile) will be presented for the EQ-5D utility index value and the EQ-5D Health Today score at 30 days post-randomization, and the difference will be tested based on t-tests or the Wilcoxon rank sum test depending on the distribution of the scores. The proportion of patients who report no problems with each of the 5 individual components of the EQ-5D (Mobility, Self-Care, Usual Activities, Pain/Discomfort, Anxiety/Depression) will be presented stratified by assigned treatment group (Table 3).

The cumulative risk of all-cause mortality through 180-day post-randomization will be estimated using Kaplan-Meier methods for all randomized patients stratified by assigned treatment group (Figure 3b). For the time-to-event analyses, follow-up will be censored at the time of withdrawal, lost-to-follow-up, or 180 days. The estimated risk at 30 days and at 180 days for each treatment group will be presented, and a log-rank statistic will be used to test the hypothesis that the mortality risk over the 180-days is equivalent in the two assigned treatment groups. The estimated risk difference (Restrictive – Liberal) and 95% confidence interval will be presented for cumulative mortality risk at 30 days and at 180 days. If neither strategy is found to be superior based on the log rank test and the 95% confidence interval for the estimated risk difference (RD) at 180-days includes 1.0, the 95% confidence interval for the 180-day mortality risk difference will be assessed using a non-inferiority margin equal to an absolute difference of

3.0%. Thus, if the entire estimated 95% confidence for the 180-day mortality RD is <3.0%, the Restrictive strategy will be considered non-inferior to the Liberal Strategy.

Missing data will not be imputed for the analyses of the secondary and tertiary hypotheses unless critical issues are noted while investigating the missing 30-day primary outcome data.

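### Hospital days, ICU days and 30-day EQ-5D are compared with no rule for deaths, so if mortality differs, the arm with more early deaths can look better on stay and, slightly, on quality of life

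*SAP*

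**What the plan says.** Tertiary aim 8 asks whether the liberal strategy "reduces each of the individual in-hospital outcomes of length of hospital stay post randomization and number of days in intensive care unit". Aim 9 asks whether it raises EQ-5D at 30 days. Fewer days and higher scores therefore count as benefit.

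- **Measure of stay (SAP, Definitions of Outcomes):** "The trial records the number of days post randomization that the patient is in the hospital and in intensive care unit". Death is not mentioned.
- **Data cut-off (SAP, Participant Follow-up):** "At hospital discharge, death or 30 days post randomization, whichever comes first, the study staff submit data related to the hospitalization". A decedent's day count therefore stops at death.
- **Summary and test for stay and ICU days (SAP, Analysis of Secondary and Other Outcomes):** "The length of hospital stay from randomization to discharge and the number of days in the ICU from randomization to discharge will be described", and "the difference will be analyzed using non-parametric Wilcoxon rank sum tests". No rank is given for deaths.
- **Test for EQ-5D (same section):** "the difference will be tested based on t-tests or the Wilcoxon rank sum test depending on the distribution of the scores". No value is given for patients who died. The Protocol (F4, 4.d) has the same gap: "Transfusion strategy comparisons of the EQ-5D quality life measures at 30 days will be based on t-tests or the Wilcoxon rank sum test".
- **Other rules that might have applied:** the assumption of no event after last contact covers the 30-day dichotomous outcomes only. Secondary and tertiary outcomes are not imputed by default. Table 3 has a row for the number with EQ-5D results but none for deaths by day 30.

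The SAP applies intention to treat to the primary, secondary and tertiary aims alike.

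**The concern.** There are two ways to read the plan for a patient who dies in hospital. If death ends the stay, a death on day 2 is a two-day stay and ranks among the best results. If a stay needs a discharge, the patient drops out and the test compares survivors only, which does not fit the intention-to-treat statement. EQ-5D is survivors-only on either reading.

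This matters here because the trial hypothesises that the liberal strategy reduces death or reinfarction, and 30-day mortality is the first secondary outcome. If the hypothesis is right, the planned comparisons for aims 8 and 9 condition on something the treatment changes, or reward it in the wrong direction. The Protocol also stresses the resource implications of the two strategies, so readers are likely to use the stay result.

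**Working it through.** **Plan's own figures.** The documents give no effect size, power or distribution for stay, ICU days or EQ-5D, so there is nothing to reproduce for these outcomes. The design effect, used below as a yardstick, does reproduce. With 1662 per arm and 18.2% versus 14.6%, z = 0.036 / √(2 × 0.164 × 0.836 / 1662) = 2.80 and power = Φ(2.80 − 1.96) ≈ 80%, as stated.

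**Mechanism.** If a decedent's stay ends at death and treatment has no other effect:

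difference in mean stay (restrictive − liberal) ≈ −(m_R − m_L) × (mean days of stay lost per death)

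The sign depends on the last factor. It is positive when deaths come early. It could be negative if patients die after stays longer than they would otherwise have had.

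**Simulation.** There were 500 trials per row, 1750 per arm (3500 at 1:1), and no treatment effect on stay or EQ-5D except through death. Assumptions not in the documents:

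- median stay 6 days, capped at 30;
- mean EQ-5D about 0.70;
- frailer patients stay longer, score lower and die more often;
- median time to death 3 or 10 days.

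Percentages count trials significant at two-sided 0.05 in the direction named, so the no-effect benchmark is 2.5%.

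| Mortality R vs L | Median day of death | Stay, R − L (days) | R shorter | EQ-5D survivors, R − L | R better | EQ-5D with death = 0, R − L | R worse |
|---|---|---|---|---|---|---|---|
| 8% vs 8% | 3 | −0.005 | 3.6% | +0.0001 | 3.0% | −0.0002 | 1.8% |
| 10% vs 8% | 3 | −0.154 | 14.2% | +0.0034 | 6.0% | −0.0104 | 18.0% |
| 10% vs 8% | 10 | −0.068 | 6.0% | +0.0024 | 4.6% | −0.0122 | 22.2% |
| 11% vs 7% | 3 | −0.322 | 43.0% | +0.0048 | 11.0% | −0.0235 | 69.6% |
| 13.0% vs 1.8% | 3 | −0.963 | 99.8% | +0.0157 | 55.8% | −0.0639 | 100% |
| 13.0% vs 1.8% | 10 | −0.478 | 42.0% | +0.0156 | 56.6% | −0.0642 | 100% |

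The formula fits. With early deaths, days lost per extra death are 0.154/0.02 = 7.7, 0.322/0.04 = 8.1 and 0.963/0.112 = 8.6. With late deaths they are 0.068/0.02 = 3.4 and 0.478/0.112 = 4.3.

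Ranking deaths below every survivor reverses the stay comparison. Restrictive is then significantly worse in 9.6% of trials at 10% vs 8% (11.0% with late deaths) and in 93.4% at the pilot rates (96.2% with late deaths).

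**Second set of assumptions.** There were 400 trials per scenario, with median stay 6 or 9 days, mean time to death 3 or 6 days, and 75% of deaths in hospital.

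- **10% vs 8%:** stay falsely significant in 5–9%, EQ-5D in 6%.
- **12% vs 8%:** restrictive stay 0.08–0.27 days shorter, significant in 8–27%; EQ-5D in 8%.
- **Pilot rates:** stay in 21–91%, EQ-5D in about 44%.

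**Limits.** The simulation in the table never lets a decedent stay longer than the same patient would have stayed alive, so it cannot show a reversal. That possibility rests on the formula. ICU days were not simulated.

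**The case against.** Several points on the other side stand.

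- **Plausible size.** The whole design effect on death or reinfarction is 18.2 − 14.6 = 3.6 points. The 12% vs 8% and 11% vs 7% cases need 4 points from death alone. The pilot's 11.2-point gap rests on 7 deaths against 1. The case nearest the design is 10% vs 8% (ratio 0.80), where the distortion is small. The EQ-5D excess there is 6.0% of trials favouring restrictive, against 3.0% at equal mortality.
- **Mortality is visible.** With 1750 per arm, the 30-day mortality test has z = 0.04 / √(2 × 0.10 × 0.90 / 1750) = 3.94 at 12% vs 8%, so power is about 98%. At 10% vs 8%, z = 2.07 and power is about 54%. The SAP says tertiary results are read against the primary one, and Table 3 prints 180-day mortality beside these outcomes.
- **Bed-days are legitimate.** As a measure of resources used, a death on day 3 is correctly three days. The difficulty is only that aim 8 treats fewer days as benefit.
- **Death-inclusive measures largely re-measure mortality.** In the second simulation, days alive and out of hospital showed a 0.74–0.90 day deficit at 12% vs 8% and was significant in 49–56% of trials, well below the mortality test.
- **A plain score of 0 is not strictly worst.** It ties deaths with survivors hospitalised for all 30 days.

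These points limit the size and shape the remedy. They do not supply the missing rule, and at 10% vs 8% the mortality test would miss the difference in nearly half of trials.

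**Conclusion.** The gap is real: neither document says how deaths enter three tertiary comparisons, and as written those comparisons can favour the arm with more early deaths. Correcting it is worthwhile but not critical. The distortion is small at a mortality difference in keeping with the design and large only at wide gaps such as the pilot's. All sizes rest on assumed distributions of stay, EQ-5D and time to death, because the documents give none.

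A reader might infer that the planned analyses will push both results towards the restrictive strategy. The documents do not support that. They do not say when deaths occur, and the direction for stay depends on it; the EQ-5D shift is slight unless mortality differs widely. Nor is any primary or secondary conclusion at risk, since these outcomes are tertiary and mortality is analysed in its own right.

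**What to change.** For aims 8 and 9, add a prespecified death-inclusive comparison and base any claim of benefit on it.

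1. **Stay and ICU.** Compare days alive and out of hospital through day 30, and index-hospitalisation ICU days with death by day 30 as the worst outcome, using the planned Wilcoxon test. Rank deaths strictly below all survivors (for example, score −1 for days alive and out of hospital), including survivors still in hospital at day 30. Confine ICU days to the index stay, because the documents do not show that ICU days during readmissions are collected.
2. **EQ-5D.** Give utility 0 and the lowest Health Today rank to patients who died before the 30-day assessment. Include deaths within the day 30–60 contact window (Protocol E4).
3. **Reporting.** Keep the planned stay and ICU figures, labelled as bed-days used, and the EQ-5D figures, labelled as survivors-only, as descriptive. Add rows to Table 3 for died, alive and assessed, and alive and not assessed.

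The cost is a paragraph in the SAP and a few lines of code. Vital status is already collected and readmission records are obtained. The downside is that the added measures mix survival with stay or quality of life and need a sentence of explanation beside the mortality result. Death-or-readmission summaries could be added for the readmission outcomes, but this point does not depend on them.
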